7.2. Secondary Efficacy Analyses

7.2.1. Endpoint / Variables

- 1) SAC TDI focal score
- 2) Assessment of respiratory daily symptoms using E-RS and its subscales
- 3) Change from baseline in SGRQ
- 4) Change from baseline in CAT
- 5) Proportion of responders according to SAC TDI focal score
- 6) Proportion of responders according to E-RS total and subscale scores
- 7) Proportion of responders according to SGRQ total score
- 8) Proportion of responders according to CAT score
- 9) Time to first on-treatment mild/moderate/severe COPD exacerbation
- 10) Time to first on-treatment moderate/severe COPD exacerbation
- 11) Time to first on-treatment severe COPD exacerbation
- 12) Time to CID composite endpoint (including individual components)
- 13) Time to CID composite endpoint excluding FEV1 (including individual components)
- 14) Mean number of inhalations of rescue use per day (using eDiary)
- 15) Percentage of rescue-free days (using eDiary)
- 16) Trough FEV1 ratio to baseline
- 17) Trough FVC
- 18) Trough IC
- 19) Subject global rating of change in COPD severity

7.2.2. Summary Measure

- 1) Mean change from BDI score
- 2) Mean change from baseline
- 3) Mean change from baseline
- 4) Mean change from baseline
- 5) Odds ratio
- 6) Odds ratio
- 7) Odds ratio
- 8) Odds ratio
- 9) Hazard ratio
- 10) Hazard ratio
- 11) Hazard ratio
- 12) Hazard ratio
- 13) Hazard ratio
- 14) Mean change from baseline
- 15) Mean change from baseline
- 16) Ratio of trough FEV1 to baseline FEV1
- 17) Mean change from baseline
- 18) Mean change from baseline
- 19) Odds ratio

7.2.3. Population of Interest

The secondary efficacy analyses will be based on the ITT population, unless otherwise specified.

7.2.4. Strategy for Intercurrent (Post-Randomization) Events

All endpoints will use the same strategy for intercurrent events as defined in Section [7.1.4](#).

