7.1.4. Strategy for Intercurrent (Post-Randomization) Events

An intercurrent event considered to have an impact on the estimand for the ITT population analysis is:

- Discontinuation of randomised treatment

- The primary treatment effect to be estimated for the ITT population will be the hypothetical effect if all subjects had stayed on their randomised treatment.

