7.2.5.1. Statistical Methodology Specification

TDI, E-RS, SGRQ-C and CAT Scores

Secondary Statistical Analysis
Endpoints

 • SAC TDI focal score • Assessment of respiratory daily symptoms using E-RS and its subscales • Change from baseline in SGRQ • Change from baseline in CAT
Model Specification, Checking and Results Presentation

 • Similar to trough FEV1 in Section 7.1.5.1. • For TDI one model will be fitted with a dependent variable of TDI and BDI in place of baseline. • For E-RS and subscales, all 4-weekly mean scores will be included in the analysis.

Responders according to TDI, E-RS, SGRQ-C and CAT Scores

Secondary Statistical Analysis
Endpoints

 • Proportion of responders according to TDI focal score • Proportion of responders according to E-RS total score • Proportion of responders according to E-RS Breathlessness score • Proportion of responders according to E-RS Cough & Sputum score • Proportion of responders according to E-RS Chest Symptoms score • Proportion of responders according to SGRQ total score • Proportion of responders according to CAT score
Model Specification

 • The proportion of responders will be analyzed using a generalized linear mixed model with treatment as an explanatory variable and visit, baseline score, stratum (no. of bronchodilators per day during run-in), geographical region, visit by baseline score and visit by treatment interactions included as covariates. • Model using proc glimmix with; random visit / subject=subject*period residual type=un statement to account for repeated visit; • For TDI the model will use BDI in place of baseline score. • For E-RS the model will use 4 weekly period in place of visit. • This analysis will include all subjects with a non-missing baseline assessment. See Section 10.6.2.3 for details on how to handle missing data.
Model Checking & Diagnostics

 • UMEC will be used as the reference level for treatment for the comparison between UMEC/VI vs. UMEC. Salmeterol will be used as the reference level for treatment for the comparison between UMEC/VI vs. Salmeterol and UMEC vs Salmeterol.

Secondary Statistical Analysis

 Pearson residuals will be plotted by using PLOTS=RESIDUALPANEL option for the model statement in SAS.
Model Results Presentation

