10.5.3. Efficacy

Spirometry
Predicted FEV₁, Absolute and Percent Reversibility in FEV₁, Percent Predicted FEV₁ and Pre-salbutamol and Post-salbutamol FEV₁/FVC Ratio

 These derived items will be delivered in a dataset from the vendor for central spirometry, except for post-salbutamol FEV₁/FVC ratio, and no recalculation will be performed. Post-salbutamol FEV₁/FVC ratio will be calculated as the ratio of post-salbutamol FEV₁ and FVC values.
Trough

 The trough value for FEV₁, FVC and IC at each of Weeks 4, 12 and 24 is calculated from the values at the assessments made 23 h and 24 h after dosing on the previous day. If the actual time of an assessment is after the time of dosing on the current day, the value for FEV₁, FVC and IC will not be used in the calculation of trough. If one of the values is missing or excluded then the trough will be the single remaining value; otherwise the trough will be the mean of the two values.

BDI/TDI

CCI - This section contained Clinical Outcome Assessment data collection questionnaires or indices, which are protected by third party copyright laws and therefore have been excluded.

SGRQ-C
CCI - This section contained Clinical Outcome Assessment data collection questionnaires or indices, which are protected by third party copyright laws and therefore have been excluded.

CAT
CAT Score

 • The CAT consists of eight items each formatted as a six-point differential scale: 0 (no impact) to 5 (high impact). A CAT score will be calculated by summing the non-missing scores on the eight items. The score can have values ranging from 0 to 40. • If one item is missing, then the score for that item is set as the average of the non-missing items. If more than one item is missing, then the CAT score will be set to missing. • If the language of the CAT conducted at a post-baseline visit is different to the language used at baseline, the CAT score for that visit and all subsequent visits will be set to missing.
CAT Responder

 • A subject will be considered a ‘responder’ according to CAT at each visit if their CAT score has decreased at least 2 units from baseline CAT score. • A subject will be considered a ‘non-responder’ if their CAT score has decreased by less than 2 units, has not changed or has increased compared to baseline. • Missing data will be handled as detailed in Section 10.6.2.

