10.6.2.3. Handling of Missing Data for Statistical Analysis

Element	Reporting Detail
Responder	
 • Subjects with a missing baseline will have responder status as missing • Subjects with missing post-baseline data at a time point and a subsequent non-missing assessment will not be considered a responder or non-responder but will be left as missing at that time point • Subjects with a missing post-baseline assessment with no subsequent non-missing assessments will be considered a non-responder for that and all subsequent time points. • Subjects with a baseline but all missing post-baseline data will be considered a non-responder at all time points.

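### The responder endpoints are declared under a hypothetical strategy but analysed with non-responder coding of all terminal missing data, including some that arises on treatment

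*SAP*

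**What the plan says.** Section 7.1.4 names one intercurrent event, "Discontinuation of randomised treatment", and targets "the hypothetical effect if all subjects had stayed on their randomised treatment". Section 7.2.4 carries this over to the secondary endpoints without exception: "All endpoints will use the same strategy for intercurrent events as defined in Section" 7.1.4. The responder endpoints for TDI, E-RS, SGRQ and CAT are items 5 to 8 of the secondary list in 7.2.1, and their summary measure in 7.2.2 is the odds ratio.

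For these endpoints Section 7.2.5.1 states: "This analysis will include all subjects with a non-missing baseline assessment. See Section 10.6.2.3 for details on how to handle missing data". Section 10.6.2.3 then sets three rules for subjects who have a baseline:

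- Terminal gap: "Subjects with a missing post-baseline assessment with no subsequent non-missing assessments will be considered a non-responder for that and all subsequent time points".
- No post-baseline data: "Subjects with a baseline but all missing post-baseline data will be considered a non-responder at all time points".
- A gap followed by a later assessment: left missing.

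Two derivations in Section 10.5.3 feed these rules. If the CAT is completed in a language different from the baseline one, "the CAT score for that visit and all subsequent visits will be set to missing". A 4-weekly E-RS period counts only if it has at least 16 diary days, and diary data after treatment discontinuation are excluded.

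**The concern.** A hypothetical strategy asks what the response would have been had the subject stayed on treatment. Counting a subject who stops as a failure makes stopping part of the outcome, which is a composite strategy. One odds ratio cannot be both.

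The coding rule also depends on whether a value is missing, not on whether treatment was stopped. Administrative gaps in subjects who are still taking study drug can therefore be recorded as failures. Neither strategy calls for that.

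Section 2.4 allows significance claims at 0.05 on all secondary endpoints once the primary comparison succeeds, so these odds ratios carry inference. If withdrawal or form completion differs between arms, an odds ratio can move away from 1 although response on treatment is the same, and the declared strategy would not tell the reader so.

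**Working it through.** **1. The sections side by side.** For a subject who discontinues and provides no later data:

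- 7.1.4 and 7.2.4 target the response that would have been seen on treatment.
- 10.6.2.3 records non-response from the first missing time point onward.

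Nothing else in the SAP reconciles the two. Section 10.6.1 sets the responder analyses apart only from a minimum-data requirement. The separate-visit models in 7.2.5.1 are a fallback for non-convergence. No responder analysis under missing at random is planned.

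**2. Missingness on treatment.**

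- *CAT language change.* That visit and every later visit are set to missing, so the gap is always terminal. The subject is a non-responder from then on, even while still on treatment.
- *E-RS.* A period under 16 diary days becomes non-response only if no later period is evaluable, for example Weeks 21-24. Completers can be affected. Appendix 1 lets Visit 5 fall 7 days early and has the eDiary collected then. With Visit 5 on Day 161, Weeks 21-24 (from Day 141) hold at most 161 − 141 + 1 = 21 days. With an assumed independent daily completion of 80%, the binomial probability of fewer than 16 days is 0.15% over 28 days and 23% over 21 days. At 90% completion the 21-day figure is 1.4%.

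**3. Dropout implied by the plan.** Section 2.3 gives 2424 randomised and about 2181 completing: 1 − 2181/2424 = 10.0%. In reverse, 2181/0.90 rounds up to 2424, so the stated numbers reproduce.

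**4. Size of the shift.** Assumptions, not from the SAP: response rate p on treatment, terminal missingness d per arm, and withdrawers who would have responded like those who stayed. The imputed proportion is then q = p(1 − d), and OR = [q1/(1 − q1)] / [q2/(1 − q2)].

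- p = 0.45 vs 0.40, no missing data (the hypothetical target): (0.45/0.55)/(0.40/0.60) = 1.23.
- Same, d = 10%/10%: q = 0.405 vs 0.360; (0.405/0.595)/(0.360/0.640) = 1.21.
- p = 0.45 in both arms, d = 8%/12%: q = 0.414 vs 0.396; (0.414/0.586)/(0.396/0.604) = 1.08, against a target of 1.00.
- Same, d = 5%/15%: q = 0.4275 vs 0.3825; (0.4275/0.5725)/(0.3825/0.6175) = 1.20 (1.205 before rounding).
- Splits reversed: 1/1.078 = 0.93 and 1/1.205 = 0.83.

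**5. Sensitivity to the last assumption.** Suppose withdrawers would have responded at 20% (assumed). With 45% among those who stay and 8%/12% withdrawal, the hypothetical proportions are 0.414 + 0.08 × 0.20 = 0.430 and 0.396 + 0.12 × 0.20 = 0.420. The hypothetical OR is (0.430/0.570)/(0.420/0.580) = 1.04, so the gap to the imputed 1.08 is about half as large.

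**The case against.** The strongest reply is that the analysis is fully specified. The responder model points to 10.6.2.3, which gives an explicit rule, so nothing is left to the programmer. Non-responder imputation is a legitimate choice. The fault then comes down to one unqualified sentence in 7.2.4, on secondary endpoints only. The scores themselves are analysed by MMRM under missing at random, so results in line with the hypothetical strategy exist for the same four instruments. This stands as to seriousness: the primary endpoint is untouched and the imputation is not wrong in itself. It does not remove the contradiction for the odds ratios, nor does it justify coding a language change as treatment failure.

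Three stronger readings are tempting, and the SAP does not support them:

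- *Every diary lapse counts as failure.* It does not. A gap followed by an evaluable period stays missing, and only terminal lapses count.
- *The odds ratios will be materially biased, or biased towards UMEC/VI.* The SAP gives no withdrawal or response rate by arm. Its own figures imply only an overall 10% dropout, and if that is equal across arms the shift is trivial. An unequal split can push the estimate either way. The trial is double blind and nothing suggests that language changes differ by arm; their frequency is not given.
- *Running the same model on observed data would recover the hypothetical effect.* The planned GLIMMIX fit uses a residual-side covariance. Unlike the likelihood-based MMRM, it is not in general valid under missing at random.

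That the report will misdescribe the odds ratios is also a prediction, not something the SAP states.

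**Conclusion.** The contradiction is real and rests on the text alone. The declared strategy for the responder endpoints is hypothetical, the analysis is composite with respect to discontinuation, and the coding rule extends to some missingness in subjects still on treatment. The CAT language case holds whenever it occurs; the E-RS case holds only for terminal periods.

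The numerical effect is conditional. It is negligible at equal 10% dropout. It reaches an odds ratio of 1.08 to 1.20, or 0.93 to 0.83 in the other direction, only under assumed unequal withdrawal with 45% response in both arms and withdrawers who would have responded like completers. These figures show what the mismatch could do and do not forecast bias in this trial. The point should be corrected because it is cheap and because these endpoints may be declared significant.

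**What to change.** - **Section 7.2.4:** exempt the responder endpoints and state a composite strategy in which discontinuation of randomised treatment or withdrawal from the study counts as non-response.
- **Section 10.6.2.3:** limit non-responder coding to time points after discontinuation or withdrawal. Leave administrative missingness on treatment (CAT language change, E-RS period under 16 diary days) as missing.
- **Optional:** if a supportive analysis under the hypothetical strategy is wanted, multiply impute the underlying score under missing at random and derive responder status from it. Do not use an observed-data rerun of the GLIMMIX model for this purpose. Once the composite strategy is declared, this analysis is not needed to cure the contradiction.

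The cost is a few sentences and a small change to the derivation. A few subjects move from non-responder to missing, and there is some extra output if the supportive analysis is run.

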7.2.5. Statistical Analyses / Methods

Details of the planned displays are provided in [Appendix 8: List of Data Displays](#) and will be based on GSK data standards and statistical principles.

Unless otherwise specified, endpoints / variables defined in Section [7.2.1](#) will be summarised using descriptive statistics, graphically presented (where appropriate) and listed.

7.2.5.1. Statistical Methodology Specification

TDI, E-RS, SGRQ-C and CAT Scores

Secondary Statistical Analysis
Endpoints

 • SAC TDI focal score • Assessment of respiratory daily symptoms using E-RS and its subscales • Change from baseline in SGRQ • Change from baseline in CAT
Model Specification, Checking and Results Presentation

 • Similar to trough FEV1 in Section 7.1.5.1. • For TDI one model will be fitted with a dependent variable of TDI and BDI in place of baseline. • For E-RS and subscales, all 4-weekly mean scores will be included in the analysis.

Responders according to TDI, E-RS, SGRQ-C and CAT Scores

Secondary Statistical Analysis
Endpoints

 • Proportion of responders according to TDI focal score • Proportion of responders according to E-RS total score • Proportion of responders according to E-RS Breathlessness score • Proportion of responders according to E-RS Cough & Sputum score • Proportion of responders according to E-RS Chest Symptoms score • Proportion of responders according to SGRQ total score • Proportion of responders according to CAT score
Model Specification

 • The proportion of responders will be analyzed using a generalized linear mixed model with treatment as an explanatory variable and visit, baseline score, stratum (no. of bronchodilators per day during run-in), geographical region, visit by baseline score and visit by treatment interactions included as covariates. • Model using proc glimmix with; random visit / subject=subject*period residual type=un statement to account for repeated visit; • For TDI the model will use BDI in place of baseline score. • For E-RS the model will use 4 weekly period in place of visit. • This analysis will include all subjects with a non-missing baseline assessment. See Section 10.6.2.3 for details on how to handle missing data.
Model Checking & Diagnostics

 • UMEC will be used as the reference level for treatment for the comparison between UMEC/VI vs. UMEC. Salmeterol will be used as the reference level for treatment for the comparison between UMEC/VI vs. Salmeterol and UMEC vs Salmeterol.

Secondary Statistical Analysis

 Pearson residuals will be plotted by using PLOTS=RESIDUALPANEL option for the model statement in SAS.
Model Results Presentation

 The odds ratio, 95% CI and p-value will be presented for UMEC/VI versus UMEC, UMEC/VI versus Salmeterol and UMEC versus Salmeterol.
Summary Results Presentation

 The number and percentage of responders and non-responders at each visit will be summarized on the same table as the analysis results details above.
Sensitivity and Supportive Statistical Analyses

 If the model fails to converge then the analyses will be carried out separately for each visit or 4 weekly period instead.

COPD Exacerbation

Secondary Statistical Analysis
Endpoints

 Time to first on-treatment mild/moderate/severe COPD exacerbation Time to first on-treatment moderate/severe COPD exacerbation Time to first on-treatment severe COPD exacerbation
Model Specification

 Cox's proportional hazards model, 
Terms in the model:
 
Dependent variable: time to first on-treatment mild/moderate/severe exacerbation or moderate/severe exacerbation or severe exacerbation
 
Categorical: treatment group, stratum (no. of bronchodilators per day during run-in) and geographical region.
 
 Use the 'exact' method for handling ties. (If the analysis will not run using the 'exact' method, then the 'Efron' method for handling ties will be used instead.)
Model Checking & Diagnostics

 The proportional hazards assumption for this method of analysis will be examined by obtaining the Kaplan-Meier estimates of the survival function $S(t)$ over time separately for treatment group. Under the assumption of proportional hazard between the treatment groups, $\ln\{-\ln[S(t)]\}$ for the two groups should be parallel to each other and the distance between them constant. If the curves are approximately parallel, then the proportional hazard assumption is not violated. If these curves cross each other or diverge greatly from the assumption of parallel lines, then the assumption is not met. If model fails to converge, model will be investigated excluding the geographical region covariate.

Secondary Statistical Analysis
Model Results Presentation

 The Hazard ratio, 95% CI and p-value will be presented for comparison between UMEC/VI versus UMEC, UMEC/VI versus Salmeterol and UMEC versus Salmeterol.

Secondary Statistical Analysis
Endpoints

 Time to first on-treatment mild/moderate/severe COPD exacerbation Time to first on-treatment moderate/severe COPD exacerbation Time to first on-treatment severe COPD exacerbation
Model Specification

 A Kaplan-Meier analysis will also be performed for figure showing Kaplan-Meier survivor functions of the proportion of subjects with a first exacerbation over time for each treatment group separately plotted on the same figure.
Model Results Presentation

 Probability of having an event, 95% CI and first quartile time to exacerbation (estimate of the time at which 25% of subjects in each treatment group would have had an exacerbation) Figure showing Kaplan-Meier survivor functions of the proportion of subjects with a first exacerbation over time for each treatment group separately plotted on the same figure.

CID

Secondary Statistical Analysis
Endpoints

 Time to first deterioration of each of the individual components i.e. Trough FEV1, SGRQ total score, CAT score, TDI focal score Time to first CID composite endpoint (SGRQ, FEV1, EXAC (mod/sev)) Time to first CID composite endpoint (CAT, FEV1, EXAC (mod/sev)) Time to first CID composite endpoint (CAT, SGRQ, TDI, EXAC (mod/sev))
Model Specification

 Cox's proportional hazards model, 
Terms in the model:
 
Dependent variable: time to endpoint of interest
 
Categorical: treatment group, stratum (no. of bronchodilators per day during run-in) and geographical region and respective baselines (i.e. endpoint includes CAT and SGRQ then include baselines for these 2 variables) .
 
 Use the 'exact' method for handling ties. (If the analysis will not run using the 'exact' method, then the 'Efron' method for handling ties will be used instead.)
Model Checking & Diagnostics

 The proportional hazards assumption for this method of analysis will be examined by obtaining the Kaplan-Meier estimates of the survival function $S(t)$ over time separately for treatment group. Under the assumption of proportional hazard between the treatment groups, $\ln\{-\ln[S(t)]\}$ for the two groups should be parallel to each other and the distance between them constant. If the curves are approximately parallel, then the proportional hazard assumption is

Secondary Statistical Analysis
not violated. If these curves cross each other or diverge greatly from the assumption of parallel lines, then the assumption is not met.
Model Results Presentation

 The Hazard ratio, 95% CI and p-value will be presented for comparison between UMEC/VI versus UMEC, UMEC/VI versus Salmeterol and UMEC versus Salmeterol.
Summary Results Presentation

 The total number of deteriorations (Yes/No) for each of the composite and the individual components for each treatment will be summarised. This will be produced for three the composite endpoint definitions.

Secondary Statistical Analysis
Endpoints

 Time to first CID composite endpoint (SGRQ, FEV1, EXAC (mod/sev)) Time to first CID composite endpoint (CAT, FEV1, EXAC (mod/sev)) Time to first CID composite endpoint (CAT, SGRQ, TDI, EXAC (mod/sev))
Model Specification

 Kaplan-Meier survivor functions of the proportion of subjects with deterioration (composite and individual components) over time will be obtained for each treatment group separately and will be plotted on the same figure.
Model Results Presentation

 Probability of having an event, 95% CI and first quartile time to CID composite endpoint (estimate of the time at which 25% of subjects in each treatment group would have had a deterioration) Figure showing Kaplan-Meier survivor functions of the proportion of subjects with a first deterioration over time for each treatment group separately plotted on the same figure.
Summary Results Presentation

 The first quartile time to first deterioration (taken from the Kaplan Meier analysis) will also be presented in a summary table.

Rescue Medication

Secondary Statistical Analysis
Endpoints

 Mean number of inhalations of rescue use per day (using eDiary) Percentage of rescue-free days (using eDiary)
Model Specification, Checking and Results Presentation

 Similar to trough FEV1 in Section 7.1.5.1 where Visit is replaced with 4-weekly period. The model will use all available values: 
 Periods defined as Weeks 1-4, 5-8, 9-12, and up to Weeks 21-24 Baseline is defined in Section 5.2 Model will include the period by baseline and period by treatment interaction. Overall treatment effect from the same model using overall main effect on Lsmean statement.
Sensitivity and Supportive Statistical Analyses

 If the assumption of normality for the percentage of rescue-free days is not satisfied, a non-

Secondary Statistical Analysis
parametric analysis of percentage of rescue-free days will be carried out. Hodges Lehman estimates for the median treatment difference and 95% CI based upon a Wilcoxon rank sum test will be used. The p-value will be based on Van Elteren test, an extension to the Wilcoxon rank sum test for two group comparison, stratified by geographical region.

Trough FEV1, FVC and IC

Secondary Statistical Analysis
Endpoints

 • Ratio of trough FEV1 to baseline FEV1 • Trough FVC • Trough IC
Model Specification

 • Ratio of trough FEV1 to baseline FEV1 at Week 24 will be analysed for the ITT population using a mixed model repeated measures (MMRM) including data recorded at each of Week 4, Week 12 and Week 24. The model will have a response of log (Trough FEV1/Baseline FEV1) with covariates of log (baseline FEV1), geographical region, stratum (no. of bronchodilators per day during run-in), visit, treatment, visit by log (baseline FEV1) and visit by treatment interactions, where visit is nominal. Results will be back transformed to provide point estimates for the ratios. • Trough FVC and Trough IC endpoints above will be analyzed using the same methodology as the primary analysis of trough FEV1 (detailed in Section 7.1) using all available FVC or IC data recorded at Weeks 4, 12 and 24 and with relevant baseline. Baseline defined in Section 5.2. 
The following will apply for all the endpoints FEV1, FVC and IC:
 
 • The Kenward and Roger method (KR) for approximating the denominator degrees of freedom and correcting for bias in the estimated variance-covariance of the fixed effects will be used. • In the event the model fails to run using the KR method, then the residual method will be used instead. • An unstructured covariance structure for the R matrix will be used by specifying 'type='UN' on the REPEATED line.
Model Checking & Diagnostics

 • Model assumptions will be applied but appropriate adjustments may be made based on the data. • Normality assumptions underlying the model used for analysis will be examined by obtaining a normal probability plot of the residuals and a plot of the residuals versus the fitted values (i.e. checking the normality assumption and constant variance assumption of the model respectively) to gain confidence that the model assumptions are reasonable. • If there are any departures from the distributional assumptions, alternative models will be explored using appropriate transformed data.
Model Results Presentation

 • Least squares (LS) mean and LS mean changes from baseline with their corresponding

Secondary Statistical Analysis

standard errors (SEs) will be presented for each treatment by visit, together with estimated treatment differences (UMEC/VI 62.5/25 vs. UMEC 62.5, UMEC/VI 62.5/25 vs Salmeterol and UMEC 62.5 vs Salmeterol), corresponding 95% CIs and p-values.
 
 • A plot of LS mean changes from baseline and 95% CIs for each treatment by visit will be generated. • A plot of LS mean treatment differences and 95% CIs between the treatment groups by visit will also be generated.
Summary Results Presentation

 • Summary of baseline FVC will be presented by treatment for all subjects. • Summary statistics for raw and change from baseline in trough FVC at each visit and for each treatment will be presented on the same table. • Summary of baseline IC will be presented by treatment for all subjects. • Summary statistics for raw and change from baseline in trough IC at each visit and for each treatment will be presented on the same table.

Subject Global Ratings of Change

Secondary Statistical Analysis
Endpoints

 • Subject global rating of COPD severity • Subject global rating of change in COPD Severity
Model Specification

 • Change of Severity will be analyzed using a generalized linear mixed model with treatment as an explanatory variable and visit, stratum (no. of bronchodilators per day during run-in), geographical region, visit by treatment interactions included as covariates.
Model Checking

 • Pearson residuals will be plotted by using PLOTS=RESIDUALPANEL option for the model statement in SAS..
Model Results Presentation

 • Number and percentage of subjects reporting each category of change at each visit • P-value for comparison between UMEC/VI 62.5/25 vs. UMEC 62.5, UMEC/VI 62.5/25 vs Salmeterol and UMEC 62.5 vs Salmeterol for change. • UMEC will be used as the reference level for treatment for the comparison between UMEC/VI vs. UMEC. Salmeterol will be used as the reference level for treatment for the comparison between UMEC/VI vs. Salmeterol and UMEC vs Salmeterol.

